### 6.3.2 Baseline Assessment of Injury

At the time of study enrollment, the subject will be interviewed about the mechanism of injury (movement that was made during injury), presence or absence previous symptoms at the injury site, presence or absence of ecchymosis and the ability to walk and run. An examination will include inspection to confirm the presence or absence of ecchymosis. Palpation of the posterior thigh will be performed with the subject in prone and the knee extended. The point of greatest pain will be marked and the distance to the ischial tuberosity will be measured and the presence or absence of a palpable defect will be recorded. Pain during resisted knee flexion will be graded on an 11 point (0 to 10) numerical pain rating scale.

Subjects will be eligible for participation in the study if the physical examination reveals: 1) localized tenderness with or without a palpable defect; 2) pain and weakness with resisted knee flexion with the individual in the prone position and 3) pain and a limitation (in comparison to the contralateral leg) in the popliteal angle with the hip at 90 degrees of flexion. Presence of a grade II/III hamstring strain will be confirmed on the baseline MRI that is performed prior to randomization. MRI evidence of a grade II/III hamstring strain includes edema with architectural disruption indicating a partial tear (grade II) or edema with complete rupture of the muscle or tendon (grade III). Excellent intra- and inter-rater reliability has been reported for this MRI grading system of acute hamstring injuries.

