### **6.4.2.2 Function and Structure of Hamstring Muscle (Specific Aim 2)**

**Pain** – An 11 point (0 to 10) numeric pain rating scale will be used to rate pain at rest and walking at the time of study enrolment and at 1, 2, 3, 4 and 6 weeks after enrolment. Pain with jogging and sprinting will be rated starting when these activities are initiated through the remainder of the in-person and telephone

follow-up visits. The numerical pain rating scale is anchored so that 0 corresponds with no pain and 10 corresponds with worst imaginable pain. The psychometric properties of the numeric pain rating scale compare favorably to other pain rating scales and are the preferred method of rating pain by young and old individuals in a study of experimentally induced pain.

**Measurement of Hamstring Flexibility** – Hamstring length will be assessed by measuring the popliteal angle as described by ten Berge et al. This will be performed by placing the ipsilateral hip at 90° of flexion and passively extending the knee to the end range of motion. To eliminate the possibility of initial muscle stiffness, the knee will be moved to end range extension 3 times before taking the measurement. A standard goniometer will be used to measure the angle of knee flexion. The proximal arm of the goniometer will be aligned with the lateral midline of the thigh on a line between the lateral epicondyle and the center of the greater trochanter of the femur and the distal arm will be positioned parallel to the lateral midline of the leg on a line between the lateral malleolus and lateral epicondyle of the femur. To account for variability between subjects, hamstring flexibility will be expressed as the difference in popliteal angle between the hamstring-injured and contra-lateral normal leg. Using this methodology, ten Berge et al demonstrated adequate levels of intra- and inter-observer reliability (ICC=.82 and .72 respectively) in healthy subjects between 20 and 29 years of age.

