#### **Specific Aim #2: Recovery of Hamstring Muscle Function and Structure.**

Recovery of muscle function will be assessed in terms of hamstring flexibility and strength. Hamstring length will be assessed by measuring the popliteal angle as described by ten Berge et al. To account for variability between subjects, hamstring flexibility will be expressed as the difference in popliteal angle between the hamstring-injured and contra-lateral normal leg. To assess hamstring strength, isometric testing with the knee flexed to 30° and 90° will be performed before treatment and at 1, 2, 3, 4 and 6 weeks and 6 months after enrolment and isokinetic testing at 60° and 180°/sec will be performed 6 weeks and 6 months after enrolment. The detailed procedures for measuring hamstring flexibility and strength are described in section 6.4.2.2.

3 Tesla MRI will be performed at enrolment and at 6 months follow-up to assess hamstring structure in terms of the length and volume of the injury and scarring. Additionally total volume of the injured and contra-lateral hamstrings will be calculated to determine the degree of atrophy. The detailed procedures for use of 3T MRI to assess hamstring structure are described in section 6.4.2.3.

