**Specific Aim #2: Recovery of Hamstring Muscle Function and Structure**

The primary endpoints to assess hamstring muscle function are the injured to contra-lateral leg differences in the popliteal angle at 6 weeks and 6 months and the injured to contra-lateral ratio of peak isokinetic hamstring torque at 6 weeks and 6 months.

The primary endpoint to assess hamstring structure will be the length and volume of fibrosis within the hamstrings at 6 months as evidence on 3 Tesla MRI.

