## **9.4        Effectiveness analysis**

The distribution of baseline characteristics and important prognostic factors (age, sex, body mass index, pre-injury activity level, etc) will be summarized overall, and by treatment (versus control) group to assess the effectiveness of the randomized allocation. Continuous variables will be summarized with means and standard deviations, and medians and inter-quartile ranges. Categorical data will be summarized using frequencies and percentages. We will then graphically explore the distributions of the primary outcome variables (for normality or skewedness and potential outliers) using q-q plots and histograms before conducting any tests to compare the two groups. When appropriate, transformations will be applied to outcome measures that are not normally distributed.

We anticipate minimal loss to follow-up (<5% of patients) at the 6 month assessment and only 10-15% loss to follow-up at 12 months post-injury. The primary outcome measures (safety and tolerance, recovery of muscle structure and function, return to prior level of function) will be evaluated between 6 weeks and 6 months; therefore the only outcome that could appreciably be affected by lost to follow-up is recurrence of injury within 12 months. We will compare baseline characteristics between participants and drop-outs, obtain reasons for

study drop (to investigate the possible missing data mechanism), and will also conduct a sensitivity analysis (assigning poor scores and good scores to those persons with missing information differentially by treatment assignment) to evaluate the impact on our study results.

For outcome variables that are measured repeatedly, we will use mixed models to adjust for correlation among the observations from the same person as well as a clustering effect for each site. In these models, subject characteristics such as age, sex, and treatment group will be fixed effect predictors, and subject and site identification will be included as random effects. Depending on the type of outcome variable of interest, we will employ linear mixed models or mixed effect logistic regression. Though we do not anticipate statistically significant differences between the Losartan and placebo groups due to the small sample size, these analyses will guide us in developing future clinical trials.

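### Section 9.4 does not pre-specify adjustment of the hamstring function models for the pre-treatment deficit, although flexibility and isometric strength are measured before treatment

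*Combined protocol and SAP*

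**What the plan says.** Section 9.4 sets the scope of the models: "For outcome variables that are measured repeatedly, we will use mixed models to adjust for correlation among the observations from the same person". It then gives their terms: "subject characteristics such as age, sex, and treatment group will be fixed effect predictors", with subject and site as random effects. No pre-treatment value, visit term or treatment-by-visit term is named. The same section says that "important prognostic factors (age, sex, body mass index, pre-injury activity level, etc) will be summarized overall, and by treatment (versus control) group". That is a descriptive comparison of the arms, and starting deficit is not among its examples.

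Section 9.1.1 (Specific Aim 2) defines the primary function endpoints as "the injured to contra-lateral leg differences in the popliteal angle at 6 weeks and 6 months", together with the injured-to-contralateral ratio of peak isokinetic torque at the same two times. Neither 9.1.1 nor 9.1.2 defines a function endpoint as change from entry. Under section 6.4.2.2, "hamstring flexibility will be expressed as the difference in popliteal angle between the hamstring-injured and contra-lateral normal leg".

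The pre-treatment data exist. Section 3.1 and its Table 1 place flexibility and isometric strength at the pre-treatment visit, and section 7.2 (Effectiveness assessments) confirms that "isometric testing with the knee flexed to 30° and 90° will be performed before treatment and at 1, 2, 3, 4 and 6 weeks". Isokinetic testing is never scheduled before treatment: Table 1 and section 7.2 give 6 weeks and 6 months, and section 6.4.2.2 adds a 4-week test.

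Section 3.2 describes 1:1 allocation in blocks of two and four and mentions no stratification by injury grade or deficit. Section 9.2 gives 10 patients per group and says the trial is meant to supply effect sizes for later power calculations.

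**The concern.** The plan collects each subject's deficit at entry but does not commit to using it. If starting deficit predicts later deficit, a chance difference between two arms of 10 is carried partly into the treatment estimate. That estimate is what the trial is meant to hand to the next one.

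Two features of the plan look as if they deal with this, but do not. Expressing flexibility as a between-leg difference removes how flexible a person naturally is, not how badly the injured leg was affected at entry. The subject random effect models correlation within a person, but does not correct the contrast between arms for a different starting point.

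The silence also leaves the role of the pre-treatment reading open. It could be a covariate, unused, or one of the repeated outcomes. In the last case, with only the named terms, a reading taken before any treatment effect can exist would contribute to the treatment coefficient.

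**Working it through.** **Inputs.** From the documents: 10 per arm (9.2), 1:1 allocation (3.2), endpoints at 6 weeks and 6 months (9.1.1). Assumed, because the documents give no value: unit SD at baseline and follow-up, and a correlation r between pre-treatment and follow-up deficit of 0.3 to 0.7. Section 9.2 gives no SD, effect size, alpha or power, so there is no sample-size calculation to reproduce.

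**1. Chance imbalance at entry.** SD of the difference in baseline means = sqrt(2/10) = 0.447 SD. P(|difference| > 0.5 SD) = 2 × [1 − Φ(0.5/0.447)] = 0.264. For more than 0.75 SD it is 0.094, and for more than 1 SD it is 0.025.

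**2. Carry-over into the unadjusted estimate.** Expected shift = r × imbalance. For a 0.5 SD imbalance:
- r = 0.3: 0.15 SD
- r = 0.5: 0.25 SD
- r = 0.6: 0.30 SD

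Simulation check (40,000 null trials, one visit): among trials with an imbalance above 0.5 SD in one given direction, the mean imbalance is about 0.73 SD. The unadjusted estimate then averages 0.22, 0.37 or 0.51 SD at r = 0.3, 0.5 or 0.7. With the covariate it averages about 0.

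**3. Whether age and sex help.** Simulation with two follow-up visits, age and sex in the model, and an assumed correlation of 0.7 between visits (1,500 trials per r). The treatment estimate correlates 0.36, 0.54 or 0.73 with the baseline imbalance at r = 0.3, 0.5 or 0.7. Adding the pre-treatment value brings this to 0.06 or less. Age and sex were simulated as unrelated to the deficit.

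**4. Precision.** Unadjusted SE = 0.447 SD. Ratio of adjusted to unadjusted SE = sqrt[(1 − r²)(1 + 1/(2n − 4))], with n = 10, so the second factor is 1 + 1/16 = 1.0625.

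| r | SE ratio | Unadjusted subjects giving the same precision (20/ratio²) |
|---|---|---|
| 0.2 | sqrt(0.96 × 1.0625) = 1.01 | 19.6 |
| 0.3 | sqrt(0.91 × 1.0625) = 0.98 | 20.7 |
| 0.5 | sqrt(0.75 × 1.0625) = 0.89 | 25.1 |
| 0.6 | sqrt(0.64 × 1.0625) = 0.82 | 29.4 |

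The lost degree of freedom raises the t multiplier from 2.101 to 2.110, which adds a further 0.4% to the interval width.

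**5. Break-even.** The SE ratio equals 1 when (1 − r²) × 17/16 = 1, so r² = 1/17 and r = 0.24. Allowing for the t multiplier gives about 0.25. With age and sex already in the model, the width ratio is 1.020 at r = 0.2 and 0.993 at r = 0.3, so break-even still lies between those values.

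**6. Pre-treatment reading as an outcome, with only the named terms.** With balanced data the treatment coefficient is the difference in subject means over all readings. With three readings (pre-treatment, 6 weeks, 6 months), a constant post-treatment effect is recovered at 2/3 of its size. With the seven readings of flexibility or isometric strength in Table 1, it is recovered at 6/7. In the three-reading case the baseline difference enters with weight 1/3 + (2/3)r, which is 0.67 at r = 0.5.

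**The case against.** The strongest reply is that r is unknown and may be low. The pre-treatment test falls within 7 days of injury (4.1), when pain may limit effort and range. Eligibility requires "pain and a limitation (in comparison to the contralateral leg) in the popliteal angle with the hip at 90 degrees of flexion", and injuries needing surgery are excluded (4.2), so the spread at entry may be narrow. Section 6.4.2.2 cites reliability of .82 (intra-observer) and .72 (inter-observer) for the popliteal angle. In section 1.2, both case-report patients, each given losartan, had normal flexibility and strength by 6 to 9 weeks, so deficits at the endpoints may be near zero. Below break-even the covariate costs precision. A shift of 0.15 to 0.30 SD is also small beside the unadjusted 95% half-width of about 2.101 × 0.447 = 0.94 SD, and section 9.2 already disclaims power. All of this stands. It limits the expected gain, but the precision loss is small too: about 1% in SE at r = 0.2.

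Stronger readings that a reader might infer are not supported:
- **That the plan rules out baseline adjustment.** The fixed effects are given as examples, so the pre-treatment value could still be added. It is unspecified, not excluded.
- **That the planned estimate is biased.** Randomisation keeps it unbiased on average. The issue is the error conditional on the imbalance in the one trial that is run.
- **That a material imbalance is likely.** At 26%, about three trials in four would have a difference below 0.5 SD.
- **That starting deficit varies widely and strongly predicts outcome.** No section says so.
- **That imbalance would go unseen.** The baseline summary in 9.4 could show it, although seeing it does not adjust the estimate.

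**Conclusion.** The point holds as a gap in pre-specification. Section 9.4 does not say whether or how the function models use the pre-treatment deficit, the data to do so are already collected, and neither the between-leg scale nor the random effect does the job.

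The size is modest and conditional: a shift of 0.15 to 0.30 SD if a 0.5 SD imbalance occurs, and an interval up to about 18% narrower at r = 0.6 but only about 2% narrower at r = 0.3. These figures rest on the assumed r and on unit SDs. For isokinetic torque no own baseline exists, so the gain there is probably smaller and has not been quantified.

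The change is still worth making. The trial's product is an effect size, the cost is small at any plausible r, and naming the covariate now prevents the choice being made after results are seen.

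**What to change.** In section 9.4, state that:
- Function models include the pre-treatment value as a fixed covariate. For flexibility this is the popliteal-angle difference. For isometric strength it is the percentage of the uninjured leg at the same, pre-named test angle (testing is done at 30° and 90°).
- For isokinetic torque, the covariate is the pre-treatment isometric percentage at one pre-named angle, described as a proxy.
- The models contain visit and treatment-by-visit terms, and treatment contrasts are reported at 6 weeks and 6 months.
- Pre-treatment readings are not treated as post-treatment outcomes. A longitudinal model that keeps them in the response with a common baseline mean for both arms is an acceptable equivalent. The plan should name one approach.

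The cost is a short amendment to 9.4 and one degree of freedom for the covariate (two if both isometric angles were used, so choose one), with a small loss of precision if r is low. No new measurement is needed. With 20 subjects the covariate list should stay short.

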#### **Specific Aim #3: To determine the effect of Losartan on time to return to prior level of function following an acute grade II or III hamstring strain.**

*Hypothesis 3:* Subjects who receive Losartan for a short duration along with the current standard of care treatment after sustaining an acute grade II or III

hamstring muscle injury will have a faster return to their prior level of sports activity when compared to the control group who receives the current standard of care treatment without Losartan.

**Specific Aim #4: To determine the effect of losartan on recurrence of injury following an acute grade II or III hamstring strain.**

*Hypothesis 4:* Subjects who receive Losartan will have a lower incidence of recurrent injury after return to their prior level of sports and military activity compared to the control group who receives the current standard of care treatment without Losartan.

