**Figure 1 – Flow Chart for Study Design**

### **3.2 Allocation to treatment**

Subjects will be randomized in a 1:1 ratio to either treatment with Losartan or placebo. Both groups will otherwise undergo the same standard of care rehabilitation for treatment of an acute hamstring injury. The randomization list will be generated using a random number generator. An equal number of subjects will be allocated to each group in random block sizes of two and four. Group assignments will be placed in sequentially numbered opaque envelopes, which will be opened by the Project Coordinator at each site once the participant has agreed to participate in the study and baseline testing has been completed to confirm subject eligibility. Thus the treatment allocation will be concealed from the Project Coordinator and others responsible for recruitment. To minimize bias throughout the study, both the subject and individuals responsible for outcome measure collection/analysis will remain blinded to the group assignment.

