## **9.2        Sample size determination**

With an approved sample size of 20 patients (10 in each group), we will not have enough statistical power to detect statistically significant differences in clinical measures between the Losartan and placebo groups. Therefore the objective of this phase 1 trial is to observe trends by group and estimate effect sizes that can be used to inform power calculations in future clinical trials.

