For time to recurrence, which will be the focus of Specific Aim 4, we expect 50%-60% of subjects in control group will have recurrence within one year. Although the subjects will report whether they had recurrence or not at intermittent time points (3, 4, 6, 9 and 12 months after treatment), we will have subjects report the actual date of recurrence. We will perform logistic regression (recurred/not recurred), and if we obtain reliable information about recurrence date and we have enough number of recurrences, we will consider Cox regression model to investigate the effect of treatment on time to recurrence, though we do not anticipate having enough power to achieve statistically significant results with either logistic or Cox modeling.

Any deviations from the previously described statistical plan will be described and justified in a protocol amendment and/or in the final report submitted to the IND application.

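### Aim 4 recurrence: the planned logistic regression has no provision for an empty cell at 10 per arm; report a risk difference with an interval and a penalised or exact odds ratio (minor, free improvement)

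*Combined protocol and SAP*

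**What the plan says.** Section 9.2 fixes the size and the purpose of the trial. "With an approved sample size of 20 patients (10 in each group), we will not have enough statistical power", it states, and the aim is therefore to look at trends by group and to "estimate effect sizes that can be used to inform power calculations in future clinical trials". Section 3.2 sets equal allocation: "Subjects will be randomized in a 1:1 ratio to either treatment with Losartan or placebo".

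For Aim 4, section 9.1.1 makes the incidence of recurrent injury the primary outcome. Section 9.4 gives the planning rate, "we expect 50%-60% of subjects in control group will have recurrence within one year", and the analysis, "We will perform logistic regression (recurred/not recurred" as the two outcome levels. Cox regression is to be considered only if recurrence dates prove reliable and there are enough recurrences. The section adds that neither model is expected to have enough power.

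No recurrence rate is given for losartan. Hypothesis 4 in section 2.1 gives only the direction: "Subjects who receive Losartan will have a lower incidence of recurrent injury after return to their prior level of sports and military activity". Section 9.4 expects "only 10-15% loss to follow-up at 12 months post-injury" and identifies recurrence as the one outcome that this loss could noticeably affect.

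No risk difference, interval method, or exact or penalised model is named for recurrence. Fisher exact tests appear only in section 9.5, for safety.

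**The concern.** With a single binary predictor, the maximum-likelihood odds ratio is finite only if each arm contains at least one subject who recurs and at least one who does not. In arms of 10 that cannot be taken for granted. When it fails, the fitted log odds ratio runs off to infinity, and software reports either a warning or a huge coefficient with a meaningless Wald interval.

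Conceding low power does not deal with this. Low power concerns whether a difference reaches significance, whereas here the planned estimate may not exist, and the trial's stated product is effect estimates for planning. The conditional Cox model does not help either: with no recurrences in one arm its partial likelihood is also monotone and the hazard ratio is not finite.

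At stake is the Aim 4 odds ratio and its interval, and the risk that a replacement method is chosen only after an empty cell has been seen.

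**Working it through.** The plan has no derived figure to reproduce: 20 is given as the approved size, without a power calculation.

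**Inputs**
- n = 10 per arm (sections 9.2 and 3.2).
- Control recurrence pc = 0.50 to 0.60 (section 9.4).
- Loss of 10-15% by 12 months (section 9.4): 10 × 0.90 = 9 and 10 × 0.85 = 8.5 evaluable per arm, so n = 9 and n = 8 are also shown.
- Losartan recurrence pt: not stated. Assumed values 0.10, 0.20 and 0.30, with 0.40 and 0.50 for a small or absent effect.

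**Formula, treatment-only model**

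An arm with rate p is all-or-none with probability s(p) = p^n + (1-p)^n. The odds ratio is infinite, zero or undefined if either arm is all-or-none:

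P = 1 - [1 - s(pc)] × [1 - s(pt)]

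**One case in full** (n = 10, pc = 0.50, pt = 0.20)
- s(0.50) = 2 × 0.5^10 = 0.00195
- s(0.20) = 0.8^10 + 0.2^10 = 0.10737
- P = 1 - 0.99805 × 0.89263 = 0.109

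**Results** (each cell: pc = 0.50 / pc = 0.60)

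| Assumed losartan rate | n = 10 | n = 9 | n = 8 |
|---|---|---|---|
| 0.50 | 0.4% / 0.8% | 0.8% / 1.4% | 1.6% / 2.5% |
| 0.40 | 0.8% / 1.2% | 1.4% / 2.1% | 2.5% / 3.5% |
| 0.30 | 3.0% / 3.4% | 4.4% / 5.0% | 6.5% / 7.4% |
| 0.20 | 10.9% / 11.3% | 13.8% / 14.3% | 17.4% / 18.2% |
| 0.10 | 35.0% / 35.3% | 39.0% / 39.4% | 43.5% / 44.0% |

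At n = 10 the control arm alone contributes only 0.2% to 0.6%. Almost all the risk comes from an empty losartan arm, so it rises with the size of the benefit.

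**Does the alternative behave better?** For this two-by-two model, Firth penalisation is the same as adding 0.5 to each cell, so an estimate always exists. Summing over all possible outcomes at n = 10 and pc = 0.55 gives these mean log odds ratios:

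| Losartan rate | True | Maximum likelihood, finite trials only | Firth, all trials |
|---|---|---|---|
| 0.30 | -1.05 | -1.12 | -1.05 |
| 0.20 | -1.59 | -1.58 | -1.58 |
| 0.10 | -2.40 | -2.02 | -2.26 |

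At a rate of 0.10, the maximum-likelihood average over trials that return a number is pulled towards zero, because the trials with the strongest result have dropped out.

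**Is the risk difference defined with an empty cell?** Take 0/10 on losartan and 5/10 on placebo. The Wilson limits are 0 to 0.2775 and 0.2366 to 0.7634, and the difference is -0.50. The Newcombe limits are:
- lower: -0.50 - √[(0 - 0)² + (0.7634 - 0.50)²] = -0.76
- upper: -0.50 + √[(0.2775 - 0)² + (0.50 - 0.2366)²] = -0.12

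The same data give no finite log odds ratio by maximum likelihood.

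**The case against.** The strongest reply is that this is rare on the plan's own figures. With control recurrence at 50-60%, an all-or-none arm occurs in about 1% of trials or fewer when there is little or no effect, and in about 3% when losartan recurrence is 30%. One trial in three needs a losartan rate of about 10%, a relative reduction of at least 80%, which the documents nowhere assume. This stands, and the frequency should not be put higher.

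A reader might also infer that Aim 4 could end with no usable estimate. The documents do not support that. The endpoint is incidence, which can be reported by arm whatever the regression does, and two proportions are what a later sample-size calculation needs. An empty arm is itself informative.

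A reader might carry age, sex and site into the recurrence model and conclude that failure is much more frequent. Section 9.4 attaches those terms to outcomes measured repeatedly, where "we will employ linear mixed models or mixed effect logistic regression" applies and site is a random effect. It names no covariates for recurrence. Moreover, separation on a covariate can leave the treatment odds ratio finite. The figures here therefore use treatment only.

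Finally, section 9.4 lets deviations be justified in an amendment or the final report, so a switch of method after an empty cell would be permitted. That is true, but the method would then be chosen with the data in view, which a sentence written now avoids.

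**Conclusion.** The point holds as a minor one. The planned odds ratio and Wald interval are not dependable for the purpose in section 9.2. The chance of a non-finite result at 10 per arm is about 3%, 11% and 35% at assumed losartan rates of 30%, 20% and 10%. With 8 or 9 evaluable per arm it is about 4-7%, 14-18% and 39-44%.

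These figures rest on the plan's 50-60% control rate, independent subjects, equal arms and a treatment-only model. The losartan rates are assumptions. Failure is uncommon for a moderate effect and concentrates where the effect is largest. It affects the odds ratio, not the availability of recurrence by arm.

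**What to change.** In the recurrence paragraph of section 9.4:
- Make the main Aim 4 summary the number and proportion with recurrence in each arm and their risk difference, with a Newcombe or exact 95% confidence interval.
- If an odds ratio is also wanted, estimate it by Firth-penalised or exact logistic regression with treatment as the only predictor, and say so in advance.

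This is a free improvement: a few lines of wording, standard software, and no new data or subjects. It should be made before unblinding.
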